**Statement of Compliance to protocol, GCP and applicable regulatory guidelines:**

This trial will be conducted in compliance with the protocol, the International Conference on Harmonization Good Clinical Practice E6 (ICH-GCP), ISO 14155, the Declaration of Helsinki, and all applicable regulatory requirements.

## CHANGE HISTORY

Version	Originator	Description of Change(s) and Section Number(s) Affected	Date
1.0	[name]	Original Protocol	14-APR-2017
2.0	[name]	Throughout protocol-updated version, date and added page numbering.  Section 6-added two additional over-label protocol numbers to Table.	17-APR-2017

████████ (5)

## SYNOPSIS

Protocol Title	Evaluation of the JJVC Investigational Toric Multifocal Contact Lens Fitting Guide Phase II
Sponsor	JJVC, [name]
Clinical Phase	Phase 2
Trial Registration	This study will be registered on ClinicalTrials.gov by the Sponsor
Test Article(s)	Investigational Products: etafilcon A Toric Multifocal Contact Lens Marketed Products: 1-Day Acuvue® Moist Brand Multifocal Contact Lens
Wear and Replacement Schedules	Wear Schedule: Daily Wear Replacement Schedule: None- Non-dispensing study
Objectives	The primary objective of this study is an evaluation of the JJVC Investigational Toric Multifocal and 1-Day Acuvue® Moist Brand Multifocal Contact Lens fitting guides by Eye Care Providers (ECPs).

[REDACTED] (5)

Study Endpoints	
Primary endpoint: The maximum number of lens modifications for both eyes required by the ECP to optimize the lenses for vision.
 
Secondary endpoint:
 
 
1. Subjective feedback from the ECP on the fitting guide process (i.e. intuitive nature of the fitting steps, adequate amount of information provided by the fitting guide, strengths and weaknesses, etc.)
 
2. Subjective feedback from the ECP regarding the layout of the fitting guide.
 
3. Surveys of the subjects experience.
 

Study Design	
This study is a single arm, non-randomized, open label, non-dispensing clinical trial. The key assessments for this study will be the number of fitting modifications and ECP feedback throughout the fit process while using the Fit Guide. Each ECP will fit at least 3 subjects and no more than 4.
 
See the flow chart at the end of the synopsis table for the schematic of the study visits and procedures of main observations.

Sample Size	
A total of approximately 32 subjects will be enrolled into the study. Approximately 24 are targeted to complete.

Study Duration	
The study duration is anticipated to be approximately 1 week.

Anticipated Study Population	
Healthy male and female volunteers with presbyopia will be screened as per criteria outlined below.

Eligibility Criteria	
Potential subjects must satisfy all of the following criteria to be enrolled in the study:
 
 
1. The subject must read, understand, and sign the STATEMENT OF INFORMED CONSENT and receive a fully executed copy of the form.
 
2. The subject must appear able and willing to adhere to the instructions set forth in this clinical protocol.
 
3. Healthy adult males or females that are at least 40 years of age and no more than 70 years of age.
 
4. The subject must either be wearing a presbyopic contact lens correction (e.g., reading spectacles over contact lenses, multifocal or monovision contact lenses, etc.) or if not respond positively to at least one symptom on the “Presbyopic
 

████████ (5)

[figure not shown]
	
Symptoms Questionnaire”.
 
5. The subject is a current soft spherical or toric contact lens wearer (defined as a minimum of 6 hours of wear per day at least two days of the week for a minimum of 1 month prior to the study).
 
6. The subject’s distance spherical equivalent or spherical component (if the eye has -1.00 to -1.50 D of refractive cylinder) of their refraction must be in the range -1.25 D to -3.75 D or +1.25 D to +3.75 D in each eye.
 
7. The subject’s refractive cylinder cannot be greater than -1.50D in either eye.
 
8. The subject’s refractive cylinder axis must be <math>90^\circ \pm 30^\circ</math> or <math>180^\circ \pm 30^\circ</math> in each eye.
 
9. The subject’s ADD power must be in the range of +0.75 D to +2.50 D in each eye.
 
10. The subject must have best corrected visual acuity of 20/20-3 or better in each eye.
 
11. The subject must have a wearable pair of spectacles if required for their distance vision.
 
Potential subjects who meet any of the following criteria will be excluded from participating in the study:
 
 
1. Ocular or systemic allergies or disease, or use of medication which might interfere with contact lens wear.
 
2. Pregnancy or lactation.
 
3. Currently diagnosed with diabetes.
 
4. Infectious diseases (e.g. hepatitis, tuberculosis) or an immune-suppressive disease (e.g. HIV).
 
5. Clinically significant (Grade 3 or 4) corneal edema, corneal vascularization, corneal staining, tarsal abnormalities or bulbar injection, or any other corneal or ocular abnormalities which would contraindicate contact lens wear.
 
6. Entropion, ectropion, extrusions, chalazia, recurrent styes, dry eye, glaucoma, history of recurrent corneal erosions.
 
7. Any previous, or planned, ocular or intraocular surgery (e.g., radial keratotomy, PRK, LASIK, lid procedures, cataract surgery, retinal surgery, etc.).
 
8. A history of amblyopia, strabismus or binocular vision abnormality.
 
9. Any ocular infection or inflammation.
 
10. Any ocular abnormality that may interfere with contact lens wear.
 

--	---

████████ (5)

	
11. Use of any ocular medication, with the exception of rewetting drops.
 
12. History of herpetic keratitis.
 
13. Participation in any contact lens or lens care product clinical trial within 30 days prior to study enrollment.
 
14. Employee of clinical site (e.g., Investigator, Coordinator, Technician)

Disallowed Medications/Interventions	Any systemic medications that may affect contact lens wear and any ocular medications with the exception of rewetting drops.
Measurements and Procedures	The key assessments for this study will be the number of fitting modifications and ECP feedback throughout the fit process while using the Fit Guide.
Microbiology or Other Laboratory Testing	None
Study Termination	The occurrence of one or more Unanticipated Adverse Device Effect (UADE), or any SAE where relationship to study agent cannot be ruled out, will result in stopping further dispensing investigational product. In the event of a UADE or SAE, the Sponsor Medical Monitor may unmask the treatment regimen of subject(s) and may discuss this with the Principal Investigator before any further subjects are enrolled.
Ancillary Supplies/ Study-Specific Materials	Eye-Cept® rewetting drops
Principal Investigator(s) and Study Institution(s)/Site(s)	A full list of Principal Investigators, clinical sites, and institutions is kept separately from the Study Protocol and is included in the study Trial Master File.

████████ (5)

**FIGURE 1: STUDY FLOWCHART**

[REDACTED] (5)

## COMMONLY USED ABBREVIATIONS AND DEFINITIONS OF TERMS

ADD	Plus Power Required For Near Use
ADE	Adverse Device Effect
AE	Adverse Event/Adverse Experience
BCVA	Best Corrected Visual Acuity
BSCVA	Best Spectacle Corrected Visual Acuity
CFR	Code of Federal Regulations
CLUE	Contact Lens User Experience
COAS	Complete Ophthalmic Analysis System
COM	Clinical Operations Manager
CRA	Clinical Research Associate
CRF	Case Report Form
CRO	Contract Research Organization
CT	Center Thickness
CTP	Clinical Technical Procedure
D	Diopter
DMC	Data Monitoring Committee
eCRF	Electronic Case Report Form
EDC	Electronic Data Capture
ETDRS	Early Treatment Diabetic Retinopathy Study
FDA	Food and Drug Administration
GCP	Good Clinical Practice
HIPAA	Health Insurance Portability and Accountability Act
IB	Investigator's Brochure
ICF	Informed Consent Form
ICH	International Conference on Harmonization
IDE	Investigational Device Exemption
IEC	Independent Ethics Committee
IRB	Institutional Review Board
ISO	International Organization for Standardization
ITT	Intent-to-Treat
JJVC	Johnson & Johnson Vision Care, Inc.
LC	Limbus Center
LogMAR ®	Logarithm of Minimal Angle of Resolution
MedDRA ®	Medical Dictionary for Regulatory Activities
MOP	Manual of Procedures
NIH	National Institutes of Health
OD	Right Eye
OHRP	Office for Human Research Protections
OHSR	Office for Human Subjects Research
OS	Left Eye

OU	Both Eyes
PD	Protocol Deviation
PHI	Protected Health Information
PI	Principal Investigator
PIG	Patient Instruction Guide
PQC	Product Quality Complaint
PRO	Patient Reported Outcome
QA	Quality Assurance
QC	Quality Control
SAE	Serious Adverse Event/Serious Adverse Experience
SAP	Statistical Analysis Plan
SAS	Statistical Analysis System
SD	Standard Deviation
SOP	Standard Operating Procedure
UADE	Unanticipated Adverse Device Effect
USADE	Unanticipated Serious Adverse Device Effect
VA	Visual Acuity

[REDACTED] (5)

## **1. INTRODUCTION AND BACKGROUND**

Johnson & Johnson Vision Care (JJVC) has recently launched a multifocal contact lens, 1-Day ACUVUE Moist Multifocal. The lens is indicated to correct  $\leq -0.75$  D of refractive cylinder. A significant number of presbyopic eyes have greater than -0.75 D of cylinder. With this in mind, JJVC has a toric multifocal lens development program to attempt to fill this need.

Historically ECPs have viewed multifocal lens fitting in general, and toric multifocal lens fitting in particular, as being difficult in terms of the excess time often required to ensure an acceptable level of vision. In addition to the extra time required to fit lenses there is often a low level of overall success. A key aspect of the fitting process is the fitting guide. The ideal fitting guide would be intuitive to the ECP, and by following the recommendations result in a high level of success, with a limited number of lens changes to reduce the time required with each patient. This study aims to evaluate the ECPs impression of the fitting guide for a novel multifocal toric lens and also their success in fitting the lenses.

### **1.1. Name and Descriptions of Investigational Products**

Investigational Products: etafilcon A Toric Multifocal Contact Lens

Marketed Products: 1-Day Acuvue® Moist Brand Multifocal Contact Lens

Both products are manufactured in etafilcon-A material and have polyvinylpyrrolidone (PVP) in the packaging solution. The lenses do differ slightly in their mechanical designs the details of which can be located in the lens Table in section 6.1 of the protocol.

### **1.2. Intended Use of Investigational Products**

The toric lens product is indicated to correct presbyopic eyes that have between -1.00 and -1.50D of refractive cylinder. The Control lens is a marketed product and is indicated to be fit on presbyopic eyes that have -0.75D of cylinder or less.

### **1.3. Summary of Findings from Nonclinical Studies**

All previous pre-clinical findings were deemed satisfactory prior to proceeding with clinical trials on humans. For the most comprehensive nonclinical information regarding the etafilcon A Toric Multifocal Contact Lens refer to the latest version of the CR-5955 Investigational Brochure. The other product used in this study is the marketed 1-Day Acuvue® Moist Brand Multifocal Contact Lens. Additional information on this lens can be found in the package insert located in the Appendices.

[REDACTED] (5)

#### **1.4. Summary of Known Risks and Benefits to Human Subjects**

The Investigational Toric Multifocal contact lenses are designed as a continuous asphere with toric correction providing for the correction of refractive ammetropia and presbyopia. The lenses have the same stabilization as the marketed 1-DAY ACUVUE® MOIST® for Astigmatism. The material is a hydrogel material, etafilcon-A, which is in the Group 4, high water, ionic polymer family and is used in the 1-DAY ACUVUE® MOIST® brand of products.

The 1-Day Acuvue® Moist Brand Multifocal Contact Lens is a currently marketed product that is also made out of the etafilcon-A material. The contact lenses are available as continuous aspheres providing for the correction of a subjects refractive ammetropia, not including astigmatism, and presbyopia.

The intent of this product is as a daily disposable contact lens that the subject wears while awake. This lens is not intended for extended wear. This evaluation is for daily disposable modality only. Anticipated risks and adverse reactions with this lens are similar to other soft daily wear contact lenses used to correct presbyopia. A listing of examples of adverse reactions is found in the Section 13 of this protocol. The Investigator should follow normal clinical guidelines in regard to examination and care of subjects who participate in this trial. For the most comprehensive clinical information regarding etafilcon A Toric Multifocal Contact Lens refer to the latest version of the etafilcon A Toric Multifocal Contact Lens Investigator Brochure. Additional details on the 1-Day Acuvue® Moist Brand Multifocal Contact Lens can be found in the package insert.

#### **1.5. Relevant Literature References and Prior Clinical Data Relevant to Proposed Clinical Study**

A PubMed search using the terms “multifocal toric contact lens fitting success”, “fitting guides and multifocal contact lenses” and “fitting multifocal contact lenses” resulted in no articles that were relevant to the aims of this study.

The lenses used in this study have been studied in a number of clinical studies (████████ and CR-5913). In addition to these studies the lenses are being evaluated in CR-5903 which is ongoing at the time of the writing of this protocol. Details with regards to these studies can be found in the latest version of the Investigator Brochure.

████ (5)

## **2. STUDY OBJECTIVES, ENDPOINTS AND HYPOTHESES**

### **2.1. Objectives**

#### **Primary Objective(s)**

The primary objective of this study is an evaluation of the JJVC Investigational Toric Multifocal and 1-Day Acuvue® Moist Brand Multifocal Contact Lens fitting guides by Eye Care Providers (ECPs).

#### **Secondary Objective(s)**

1. Subjective feedback from the ECP on the fitting guide process (i.e. intuitive nature of the fitting steps, adequate amount of information provided by the fitting guide, strengths and weaknesses, etc.)
2. Subjective feedback from the ECP regarding the layout of the fitting guide.
3. Surveys of the subjects experience.

#### **Exploratory Objective(s) Not Applicable**

### **2.2. Endpoints**

The endpoints will be the number of lenses required for optimization of vision (i.e. ease of fit) and subjective responses from the ECPs regarding the materials/process used for fitting the lenses as well as subjective responses from the subjects.

#### **Primary Endpoint(s)**

Number of lenses required to optimize vision.

#### **Secondary Endpoint(s)**

1. Subjective feedback from the ECP on the fitting guide process (i.e. intuitive nature of the fitting steps, adequate amount of information provided by the fitting guide, strengths and weaknesses, etc.)
2. Subjective feedback from the ECP regarding the layout of the fitting guide.
3. Surveys of the subjects experience.

#### **Other Observation(s)**

### **2.3. Hypotheses**

#### **Primary Hypotheses**

The maximum number of modification required by the ECP to optimize vision will not exceed one modification in more than 50% of the subjects.

Secondary Hypotheses  
Not Applicable

Other Hypotheses  
Not Applicable

### **3. TARGETED STUDY POPULATION**

#### **3.1. General Characteristics**

Healthy male and female volunteers who are presbyopic will be recruited for the study. The subjects will all be adapted wearers of soft contact lenses in both eyes.

#### **3.2. Inclusion Criteria**

Potential subjects must satisfy all of the following criteria to be enrolled in the study:

1. The subject must read, understand, and sign the STATEMENT OF INFORMED CONSENT and receive a fully executed copy of the form
2. The subject must appear able and willing to adhere to the instructions set forth in this clinical protocol.
3. Healthy adult males or females that are at least 40 years of age and no more than 70 years of age.
4. The subject must either be wearing a presbyopic contact lens correction (e.g., reading spectacles over contact lenses, multifocal or monovision contact lenses, etc.) or if not respond positively to at least one symptom on the “Presbyopic Symptoms Questionnaire”.
5. The subject is a current soft spherical or toric contact lens wearer (defined as a minimum of 6 hours of wear per day at least two days of the week for a minimum of 1 month prior to the study).
6. The subject’s distance spherical equivalent or spherical component (if the eye has -1.00 to -1.50 D of refractive cylinder) of their refraction must be in the range -1.25 D to -3.75 D or +1.25 D to +3.75 D in each eye.
7. The subject’s refractive cylinder cannot be greater than -1.50D in either eye.
8. The subject’s refractive cylinder axis must be  $90^\circ \pm 30^\circ$  or  $180^\circ \pm 30^\circ$  in each eye.
9. The subject’s ADD power must be in the range of +0.75 D to +2.50 D in each eye.
10. The subject must have best corrected visual acuity of 20/20^3 or better in each eye.
11. The subject must have a wearable pair of spectacles if required for their distance vision.

████████ (5)

### **3.3. Exclusion Criteria**

Potential subjects who meet any of the following criteria will be excluded from participating in the study:

1. Ocular or systemic allergies or disease, or use of medication which might interfere with contact lens wear.
2. Pregnancy or lactation.
3. Currently diagnosed with diabetes.
4. Infectious diseases (e.g. hepatitis, tuberculosis) or an immune-suppressive disease (e.g. HIV).
5. Clinically significant (Grade 3 or 4) corneal edema, corneal vascularization, corneal staining, tarsal abnormalities or bulbar injection, or any other corneal or ocular abnormalities which would contraindicate contact lens wear.
6. Entropion, ectropion, extrusions, chalazia, recurrent styes, dry eye, glaucoma, history of recurrent corneal erosions.
7. Any previous, or planned, ocular or intraocular surgery (e.g., radial keratotomy, PRK, LASIK, lid procedures, cataract surgery, retinal surgery, etc.).
8. A history of amblyopia, strabismus or binocular vision abnormality.
9. Any ocular infection or inflammation.
10. Any ocular abnormality that may interfere with contact lens wear.
11. Use of any ocular medication, with the exception of rewetting drops.
12. History of herpetic keratitis.
13. Participation in any contact lens or lens care product clinical trial within 30 days prior to study enrollment.
14. Employee of clinical site (e.g., Investigator, Coordinator, Technician)

### **3.4. Enrollment Strategy**

Study subjects will be recruited from the potentially eligible subjects identified in the clinical site's subject database.

## **4. STUDY DESIGN AND RATIONALE**

### **4.1. Description of Study Design**

This study is a single arm, non-randomized, open label, bilateral, non-dispensing clinical trial. There is one study visit. Each subject will wear lenses for approximately 30-90 minutes. The key assessments for this study will be the number of fitting modifications and ECP feedback throughout the fit process while using the Fit Guide. Each ECP will fit a maximum of 4 subjects a. At the conclusion of the study subjects will not have access to the investigational lenses. The marketed Moist Multifocal lenses can be obtained from their own

[REDACTED] (5)

ECP, at the subjects discretion, however no marketed product or contact lens prescriptions will be given to the subject to use outside of this clinical trial.

#### **4.2. Study Design Rationale**

The primary aim of the study is to obtain ECP feedback on the fitting process of the lenses. With this aim in mind, the study design attempts to create the typical multifocal contact lens fitting scenario encountered in routine clinical practice. The primary purpose of the study is to obtain feedback on the ease of fitting and fitting guide for the multifocal toric lenses and as such there is no need for a Control lens or masking of any of the study personnel.

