#### **5.2. Masking**

The study is open label with no masking. Subjects will be aware of the identity of the investigational product. Investigators and clinical site personnel involved in the data collection will not be masked as to the identity of the investigational product.

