1.21	Lens Fit Assessment	
The principal or Co-Investigator will evaluate the general lens fit. Lens fit will be assessed in primary gaze, upgaze & Josephson push up test.
 
An unacceptable lens fit will be any one or more of the following:
 
 
• presence of limbal exposure (appearance of clear cornea) in any gaze
 
• presence of edge lift
 
• Presence of unacceptable movement (excessive or insufficient) in all three movement categories (primary gaze, upgaze, and push-up).
 
 
If either lens is deemed unacceptable, the subject will be discontinued from the study. Perform a slit-lamp evaluation and complete the Final Evaluation
	

████████ (5)

1.22	Lens Settling	Allow the study lenses to continue to settle for a minimum of 15 minutes from the time of lens insertion	
1.23	ECP Fitting with Fit Guide	The ECP will be provided the fitting guides and assess the vision provided by the lenses and will determine if a lens change is needed. The fitting activities of the ECP will be videotaped. During the fitting of the lenses the ECP may use the slit lamp to evaluate the fit of the lens. .	Appendix F/G Fitting Guides
1.24	Modifications (if necessary)	If the ECP determines a change in lenses is required they will be allowed two Modifications. If modification is needed complete steps 1.18 to 1.19 for each lens change.	Appendix F/G Fitting Guides
1.25	Post-Fit Questionnaire	The subject will evaluate the vision characteristics, comfort characteristics, handling characteristics, and visual symptoms of the study lenses using the PRO questionnaire. Subjects will also be shown a product concept of the lens they have just worn and their feedback regarding the concept will be collected.	Appendix A and H
1.26	Exit Biomicroscopy	The Principal Investigator or Co-Investigator will perform biomicroscopy OD and OS. Slit Lamp Classification Scales will be used to grade the findings. For the conjunctival redness [REDACTED] 0.5 unit increments will be used in the grading. Corneal Staining Assessment [REDACTED] will be graded in 1.0 increments.	[REDACTED]
1.27	ECP Interview	The ECP will be interviewed regarding their experience fitting the subject using the Fit Guide.	Appendix I

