#### **14.5. Primary Analysis**

Primary efficacy analysis:

Due to the potential low incidence rates of unacceptable lens fitting, summary statistics will be firstly used to evaluate the percentage of the subjects with at most one optimization per-protocol population.

Due to the potential low incidence rates of unacceptable lens fitting, summary statistics will be firstly used to evaluate the percentage of the subjects with at most one optimization per-protocol population.

If applicable, a generalized linear mixed model with a binary distribution and logit link function will be applied to the number of modifications (1=at most one modification; 0 = more than one modification). Age, gender and subjects' add power will be included in the model as fixed effects when appropriate. ECP and subject will be included as random effect.

The proportion of subjects with at most one optimization will be calculated with 95% confidence interval. If the lower limit of the confidence interval is greater than 50%, the statistical superiority will be concluded.

[REDACTED] (5)

If the incidence rate is too low or there are problems with the convergence of the above model, Agresti methods or Fisher's exact test for binomial proportion will be used to evaluate the confidence intervals of the corresponding endpoints.

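### The primary endpoint is the fitting ECP's own decision, and nothing visible in the plan keeps the at-most-one success cut or the 50% criterion from the ECPs

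*Combined protocol and SAP*

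**What the plan says.** The Synopsis defines the primary endpoint as "The maximum number of lens modifications for both eyes required by the ECP to optimize the lenses for vision". In Section 7.2, step 1.23, the ECP works with the fitting guides to "assess the vision provided by the lenses and will determine if a lens change is needed". Step 1.24 adds: "If the ECP determines a change in lenses is required they will be allowed two Modifications". Section 14.5 codes the outcome as "1=at most one modification; 0 = more than one modification" and concludes superiority when the lower 95% confidence limit for the success proportion lies above 50%. The hypothesis in Section 2.3 is: "The maximum number of modification required by the ECP to optimize vision will not exceed one modification in more than 50% of the subjects".

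On masking, Section 4.2 reasons that the purpose is feedback on ease of fitting and on the guide, so "there is no need for a Control lens or masking of any of the study personnel". Section 5.2 says "The study is open label with no masking" and goes on to explain this in terms of who knows which product is being worn. Neither section mentions knowledge of the hypothesis or of the success cut. Section 16.3 makes the Principal Investigator responsible for seeing that sub-investigators and site personnel know the protocol.

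**The concern.** The outcome is a person's decision, and the person who makes it may know how it will be scored. With the cap of two, success and failure differ only in whether the ECP asks for a second change. The visible visit steps set no acuity level at which vision counts as optimised, and they record no acuity with the study lenses on the eye. Fitting is videotaped and the subject rates vision afterwards, but the plan uses neither to check the modification decision.

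An ECP who knows that a second change counts as failure could let a marginal one go, and that subject would then be scored a success. There is no control arm in which such a shift could cancel. The ECP random effect in Section 14.5 describes differences between ECPs and does not remove a shift that they share. At stake is whether the superiority statement reflects the fitting guide or the ECPs' awareness of the target.

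**Working it through.** **Inputs from the documents.** Completers: 24 (Section 14.2). Cap: two modifications (step 1.24). Success: at most one (Section 14.5). Decision rule: lower 95% limit above 50% (Section 14.5). Subjects per ECP: three to four (Synopsis).

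**The plan's own figures.** The power table in Section 14.2 reproduces with an exact binomial test against 50% at one-sided 5%:

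| True rate | N | Cut | Power computed | Power stated |
|---|---|---|---|---|
| 70% | 56 | 35 | 0.9126 | 0.913 |
| 75% | 35 | 23 | 0.9244 | 0.924 |
| 80% | 23 | 16 | 0.9285 | 0.928 |

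This point disputes none of those numbers.

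**Success counts at n = 24.** The lower limit of a two-sided 95% interval gives:

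- Agresti-Coull: 46.6% at 16/24 and 50.6% at 17/24, so success needs at least 17.
- Clopper-Pearson: 48.9% at 17/24 and 53.3% at 18/24, so success needs at least 18.

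Section 14.5 names Agresti methods as a fallback to the mixed model and does not fix one interval, so both rules are carried. Clustering by ECP and the model covariates are ignored.

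**Sensitivity to forgone second changes.** Let p be the true success rate and f the share of needed second changes that are not made. The observed rate is p′ = p + f(1 − p). The documents give no value for f; 10% to 25% is an assumption, applied equally to all ECPs. The chance of declaring success is P(X ≥ r) for X ~ Binomial(24, p′).

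- f = 10%, p = 0.50: p′ = 0.50 + 0.10 × 0.50 = 0.55.
- f = 25%, p = 0.50: p′ = 0.50 + 0.25 × 0.50 = 0.625.
- f = 25%, p = 0.60: p′ = 0.60 + 0.25 × 0.40 = 0.70.

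| True p | f | p′ | r = 17 | r = 18 |
|---|---|---|---|---|
| 0.50 | 0 | 0.50 | 3.2% | 1.1% |
| 0.50 | 10% | 0.55 | 8.6% | 3.6% |
| 0.50 | 25% | 0.625 | 26.8% | 14.5% |
| 0.60 | 0 | 0.60 | 19.2% | 9.6% |
| 0.60 | 25% | 0.70 | 56.5% | 38.9% |

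**In subjects.** At p = 0.50, 12 of 24 would need a second change. The assumed range is 12 × 0.10 = 1.2 to 12 × 0.25 = 3 subjects. One subject is 1/24 = 4.2 percentage points; one ECP with four subjects is 4/24 = 16.7 points.

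**The case against.** A reader might infer that Section 4.2, by rejecting masking, exposes the success cut to the ECPs. It does not. The masking rejected there and in Section 5.2 is masking to product identity, and hiding the product would not hide the cut. No passage says that ECPs are told the hypothesis. Section 7.2 gives the toric and general fit assessments to the principal or co-investigator and treats the ECP as a separate fitter who receives the guide. Whether ECPs count as site personnel under Section 16.3 is not settled. All of this stands, and it limits the point to a missing safeguard.

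The ECP's discretion may also be narrower than it looks. Appendices F and G are redacted, which is no fault of the plan, and the visible package-insert guidance for the marketed lens is stepwise. This stands too, although step 1.24 still leaves the determination to the ECP.

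Two further readings go too far. One is that any bias must favour the hypothesis and could not be repaired. Nothing in the documents gives ECPs a stake in success, and one who is videotaped and asked for the guide's weaknesses might make an extra change instead. The recordings could also support independent review, though none is planned. The other is that ECPs who have already used either guide should be barred. The multifocal lens is already marketed, its guide is part of the primary objective, and Section 4.2 wants to mirror routine practice, so such a bar could remove typical fitters. The text is silent on who may serve as an ECP, and that does not show that unsuitable people would.

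Finally, the study is a one-visit, non-dispensing study aimed mainly at feedback, and its size was not set by power. That lowers the stakes, but the plan still tests a hypothesis and will claim superiority on this endpoint.

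**Conclusion.** The point holds as an avoidable risk of bias. The endpoint is the ECP's judgement, failure requires a chosen second change, and no visible passage keeps the success cut or the 50% criterion from the person making that choice. The documents do not establish that ECPs know the cut, that they would act on it, or in which direction.

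The size is a matter of sensitivity. At a true rate of 50%, a change of about one to three subjects' classification, if it ran towards success, would raise the chance of a false superiority claim roughly threefold at the lower end (3.2% to 8.6%, or 1.1% to 3.6%) and to 26.8% or 14.5% at the upper end. These figures rest on the assumed 10% to 25% forgone, on 24 completers, and on independent subjects. They are not a forecast.

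**What to change.** Keep product identity open. Replace the masking clause in Section 4.2 and add to Section 5.2 wording such as:

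> Fitting ECPs are not told the primary hypothesis, the at-most-one cut or the 50% criterion; they are told only to optimise vision with the guide as they would in practice.

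Add a matching exception for fitting ECPs to the protocol-familiarity requirement in Section 16.3. This has to be in place before the first fitting, since an ECP who has learned the cut cannot be made unaware of it. It also serves the routine-practice aim of Section 4.2.

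The cost is a separate ECP briefing sheet and restricted access to the protocol for the fitting ECPs. No subjects or visit procedures are added.
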